Subjects will attend weekly visits during the 3-week study drug withdrawal period. Assessment of potential withdrawal effects of dasotraline will be conducted via administration of the CSSA, DESS, HAM-A, and MADRS at the end of treatment. Subjects will undergo assessments every other day and weekly as follows: The CSSA and DESS will be completed every other day during the 3-week study medication withdrawal period. Clinical site staff will call the subject every other day, beginning the second day after the last dose of study drug, unless a clinic visit is scheduled for that day. Phone contacts may be made up to 3 times per day if the clinical site staff are unable to contact the subject on the first 2 attempts. If the subject cannot be contacted on a given day, during the next contact the study site staff will retrospectively collect the missed CSSA and DESS, in addition to the current day's CSSA and DESS, as necessary. Clinical site staff will record the responses in the subject's source information and in the case report form (CRF) with the contact date and time. The CSSA, DESS, HAM-A, and MADRS also will be administered at each weekly visit during the withdrawal period.

A window of ± 1 day will be allowed for each weekly clinic visit and telephone call during the study medication withdrawal period.

After the last withdrawal period visit, all subjects will be referred for follow-up care as determined by the investigator.

A study schematic is presented in Figure 1. Details of the study assessments and other procedures to be performed at each visit are presented in Table 2, Schedule of Assessments, and Section 11, Study Assessments.

If necessary, subjects may return to the clinic at any time for an unscheduled visit.

Figure 1: Study Schematic

Study Schematic

^a There will be no break in study drug treatment between the core study and this extension study.

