11.5.3. Withdrawal Period

All subjects, including those who complete treatment and those who discontinue treatment, will complete weekly in-clinic visits during the 3 week study medication withdrawal period. In addition to the weekly visits, the CSSA and DESS will be completed during the 3 week study medication withdrawal period on non-clinic visit days. Clinical site staff will call the subject every other day during the study medication withdrawal period, beginning the second day after the last dose of study drug, unless a clinic visit is scheduled for that day (up to 3 times per day if the clinical site staff are unable to contact the subject on the first 2 attempts). Clinical site staff will record the responses to the CSSA and DESS in the subject's source information and in the CRF with the contact date and time. During these calls, clinical site staff will also record AE(s) and concomitant medications.

A window of ± 1 day will be allowed for each weekly clinic visit and telephone call. If the subject cannot be contacted on a given day, during the next contact the study site staff will

retrospectively collect the missed CSSA and DESS, in addition to the current day's CSSA and DESS, as necessary.

11.5.3.1. Visit 16E (Week 53; Day 371 ± 1^5) and Visit 17E (Week 54; Day 378 ± 1^6)

The following study related procedures will be performed:

- Record concomitant medications
- Collect vital signs and weight
- Perform ECG
- Record AEs
- Administer Scales: MADRS, C-SSRS, BE-CGI-S, HAM-A, CSSA, and DESS

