6.1.1.2. Withdrawal Period (Off Treatment)

The withdrawal period will begin with immediately after the last study dose. Study day relative to the last study dose date will be denoted as Day 0. The end of the withdrawal period is defined as the maximum of last study visit (scheduled or unscheduled) and last phone contact after the

322

last study dose. If the last study dose date is missing or ‘unconfirmed’ (eg, lost follow-up subjects), start and end days relative to the last study dose will be set as missing.

Each subject’s assessment at each visit (site or phone contact) in the withdrawal period will be assigned a study day with respect to start date of the withdrawal period (ie, the last study dose date).

- Study Day = Assessment date – the last dose date if assessment date \geq the last dose date in the extension study

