6.1.2.2. Visit Window for Visits in Withdrawal Period

Visits within withdrawal period will be mapped per visit window defined in [Table 5.1](#) below for effectiveness and safety data collected in withdrawal period except of the phone contact visits used for collecting additional CSSA and DESS information.

Table 5.1: Visit Window for Clinic Visits in Withdrawal Period

Variables to be Applied	Time Interval (Day) ^a	Target Time Point (Day)	Analysis Visit (label on output)
CSSA, DESS	-5 to 1 ^(b)	0	Withdrawal Baseline
	2 – 10 ^(c)	7	Withdrawal Week 1
	11 – 17 ^(c)	14	Withdrawal Week 2
	18 – EOS ^(c)	21	Withdrawal Week 3
Other	-5 to 3	0	Withdrawal Baseline
	4 – 10	7	Withdrawal Week 1
	11 – 17	14	Withdrawal Week 2
	18 – EOS	21	Withdrawal Week 3
^a Relative to the day of the last dose of open-label study medication ^b per both phone contacts or clinic visits ^c for clinic visits only.			

If a subject has 2 or more visits in one analysis visit window, the visit closest to the targeted day will be used as the study visit for that analysis visit window. The other additional visit(s) will be denoted as unscheduled visit and not included in the by-visit descriptive summary analyses. However, measurements from this/these other additional visit(s) may be included in the other safety analyses to assure all off-treatment measurements are included. If 2 study visits occur the same number of days from the target day within the same visit window, the later one will be considered as the study visit for that target day.

Non-clinic phone contact visits within withdrawal period will be mapped per visit window defined in [Table 5.2](#) below for CSSA and DESS specifically.

Table 5.2: Visit Window for Non-Clinic/Phone Contact Visits in Withdrawal Period

Variables to be Applied	Time Interval (Day) ^a	Target Time Point (Day)	Analysis Visit (label on output)
CSSA, DESS	1 – 2	1	Day 1-2
	3 – 4	3	Day 3-4
	5 – 6	5	Day 5-6
	7 – 8	7	Day 7-8
	9 – 10	9	Day 9-10
	11 – 12	11	Day 11-12

322

	13 – 14	13	Day 13-14
	15 – 16	15	Day 15-16
	17 – 18	17	Day 17-18
	19 – 20	19	Day 19-20
	21 – 22	21	Day 21-22
	23 – 24	23	Day 23-24
	25 – EOS ^(b)	25	≥ Day 25
^a Relative to the day of the last dose of open-label study medication			
^b per phone contacts visits only.			

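### SAP Table 5.2 targets each CSSA/DESS phone contact one day before its scheduled call, so a late call can displace the next on-time call in the by-visit summaries

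*SAP*

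**What the plan says.** **Call schedule.** Protocol 7.1: "Clinical site staff will call the subject every other day, beginning the second day after the last dose of study drug". Protocol 11.5.3 repeats this and adds: "A window of ± 1 day will be allowed for each weekly clinic visit and telephone call".

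**Day numbering.** SAP 6.1.1.2: "Study day relative to the last study dose date will be denoted as Day 0". Its formula is "Study Day = Assessment date – the last dose date if assessment date" is on or after that date, with no day added.

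**Windows.** SAP 6.1.2.2, "Table 5.2: Visit Window for Non-Clinic/Phone Contact Visits in Withdrawal Period", uses two-day intervals with the target on the first day of each: 1–2 (target 1), 3–4 (target 3), 5–6 (target 5), up to 23–24 (target 23), then 25 to end of study (target 25).

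**Selection.** The same section says that where a window holds two or more visits, "the visit closest to the targeted day will be used as the study visit for that analysis visit window", with ties going to the later one. The others are "not included in the by-visit descriptive summary analyses", although they may enter other safety analyses.

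**Use.** SAP 7.4.6.2 summarises CSSA and DESS by these day bins, interleaved with Withdrawal Weeks 1 to 3.

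**The concern.** The target column decides which record is kept when two contacts share a window. Here each target lies one day before the scheduled call, and each scheduled day is the last day of its window. A call made one day late, which the protocol permits, therefore moves into the next window and lands exactly on that window's target. The next call, made on its proper day, is one day off target and loses.

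Withdrawal effects measured by CSSA and DESS are a secondary objective, and the phone calls supply the only CSSA and DESS scores between the weekly clinic visits. The by-visit tables would leave out some correctly timed scores and show some bins as missing although a contact took place.

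**Working it through.** **1. Scheduled days.** The last dose is Day 0, so the second day after it is Day 2. Calls every other day over three weeks, leaving out the Day 14 clinic visit, fall on Days 2, 4, 6, 8, 10, 12, 16, 18 and 20: nine calls. The Table 5.2 targets for these windows are 1, 3, 5, 7, 9, 11, 15, 17 and 19. Each is the scheduled day minus 1. Counting the day of the last dose as the first day would put calls on Days 1, 3, 5 and match the targets, but that contradicts both the protocol's start of calling and SAP 6.1.1.2.

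**2. The rule applied to simple patterns.**

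- All on time: each call falls in its own window and nothing is dropped.
- All one day early: the same.
- Day 2 call made on Day 3, Day 4 call on time: both fall in window 3–4. Distances to target 3 are |3 − 3| = 0 and |4 − 3| = 1. The late call is kept, the on-time call is dropped, and window 1–2 is empty.
- All one day late: nothing is dropped, each score moves one bin later, and windows 1–2 and 15–16 are empty.

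Of the nine timing combinations (early, on time, late) for two consecutive calls, only late followed by on time drops an on-time call.

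**3. Size.** The documents give no rate of late calls, so the rates below are assumptions. Let p be the chance that a call is one day late and e the chance that it is one day early, independently, around a fixed grid of days. The nine calls contain seven pairs two days apart (2–4, 4–6, 6–8, 8–10, 10–12, 16–18, 18–20). Windows 1–2 and 15–16 have no preceding call that could fill them.

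- On-time calls displaced per subject = 7p(1 − p − e)
- Empty windows per subject, of nine = 2p + 7p(1 − p)

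| p late | e early | Displaced | Share of 9 | Empty | Share of 9 |
|---|---|---|---|---|---|
| 5% | 0 | 7 × 0.05 × 0.95 = 0.33 | 3.7% | 0.10 + 0.33 = 0.43 | 4.8% |
| 10% | 0 | 7 × 0.10 × 0.90 = 0.63 | 7.0% | 0.20 + 0.63 = 0.83 | 9.2% |
| 10% | 10% | 7 × 0.10 × 0.80 = 0.56 | 6.2% | 0.83 | 9.2% |
| 20% | 0 | 7 × 0.20 × 0.80 = 1.12 | 12.4% | 0.40 + 1.12 = 1.52 | 16.9% |
| 20% | 20% | 7 × 0.20 × 0.60 = 0.84 | 9.3% | 1.52 | 16.9% |
| 30% | 0 | 7 × 0.30 × 0.70 = 1.47 | 16.3% | 0.60 + 1.47 = 2.07 | 23.0% |

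Simulating the allocation rule with late calls only gives the same values to within sampling error (0.63 and 0.83 at 10%).

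**4. Candidate corrections.**

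- *Targets 2, 4, 6 with the same intervals.* In the Day 3 / Day 4 case the distances to target 4 are 1 and 0, so the on-time call is kept. Displaced on-time calls fall to 0 at every p. The empty windows remain (0.83 per subject at 10%), because they come from the interval edges.
- *Intervals 2–3, 4–5 with targets 2, 4.* Late calls stay in place, but a Day 4 call made on Day 3 now falls in 2–3, is dropped when the Day 2 call was on time, and leaves 4–5 empty.

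A two-day interval cannot hold a range of ±1 day, which spans three days.

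**The case against.** The strongest reply is that this is a small misalignment in a supplementary descriptive display. Much of that stands.

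- A reader might infer that on-time calls are routinely lost. They are not: the fault needs a late call followed by an on-time one.
- A reader might infer that scores are discarded. The loss is from the by-visit summaries only. The SAP lists all data, lets unselected contacts enter other safety analyses, defines DESS worst-case summaries over the whole withdrawal period, and takes the Withdrawal Endpoint from the last non-missing score, clinic or phone.
- A reader might infer that the withdrawal endpoints are compromised. The protocol's named endpoints are the scores at Weeks 53, 54 and 55. For CSSA and DESS, Table 5.1 maps those from clinic visits only, so Table 5.2 does not touch them. Nor do the documents say that the call series is there to locate a symptom peak.
- The bins are labelled by actual day, so a Day 3 score shown under Day 3–4 is correctly labelled.
- If a contact is missed, the next one also collects the missed CSSA and DESS. If that record carries the missed day's date, the window is filled. The SAP does not say which date is used. This does not help a call simply made on Day 3 with no retrospective record.
- The protocol does not say whether the sequence restarts after a late call. If Day 3 is followed by Day 5, nothing is displaced, and the percentages above would be too high.
- The selection rule is printed after Table 5.1 and before Table 5.2. Its wording is general, and a target column has little purpose without it, so applying it to Table 5.2 is the natural reading. If it was not meant to apply, Table 5.2 has no selection rule.

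None of this explains why the targets precede the scheduled calls.

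**Conclusion.** The mismatch follows from the documents alone: every Table 5.2 target for a scheduled call is one day early, and for a late call followed by an on-time call the rule keeps the wrong record in the by-visit CSSA and DESS summaries. The empty windows have a separate cause, the two-day intervals.

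Only the size rests on assumptions: nine calls, a fixed grid, independent one-day deviations, no retrospective record filling the gap, and an assumed late rate. On those terms, 10% late gives about 9% of windows empty and 6–7% displaced; 20% late gives about 17% and 9–12%. The lower displaced figures apply when as many calls are early as late.

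This is worth correcting before the final database lock. It concerns a secondary, descriptive analysis and leaves the primary safety objective untouched.

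**What to change.** 1. In SAP Table 5.2, change the targets to Days 2, 4, 6 and so on, and state that the closest-to-target rule applies to that table. This stops on-time calls being displaced. It costs one table edit and one sentence, and needs no new data.
2. To avoid empty windows as well, allocate each record by its scheduled contact, or by the missed day for retrospectively collected scores, where the CRF identifies it. Calendar distance alone cannot do this, because Day 3 is within one day of both Day 2 and Day 4. The protocol asks sites to record the contact date and time and mentions no contact number, so check first what the CRF holds. Where it does not identify the contact, keep the actual-day bins.
3. State which date a retrospectively collected score carries.

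The drawback of step 2 is that a label may differ by one day from the actual day since the last dose. Step 1 alone does not have that drawback, but leaves the empty windows.

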6.1.3. Baseline

Three types of Baseline will be defined: DB Baseline, OL Baseline, and Withdrawal Baseline.

6.1.3.1. DB Baseline

DB Baseline (ie, Baseline assessment of the double-blind core studies [SEP 360-221, or SEP 360-321]) is defined as the last assessment made on or before the 1st dose of double-blind study medication as described in the SAPs of the core studies.

6.1.3.2. OL Baseline

Except for height (for all subjects), demographics (for all subjects) and EDE-Q modified (for subjects continued from SEP360-221), unless otherwise specified, based on the protocol of SEP360-322 and the schedule of assessment ([Attachment 9.1](#)), OL Baseline values are to be carried over from W12/Endpoint in the core studies. The OL Baseline is defined as the last assessment made on or before Day 1 of the extension study (ie, Baseline assessment in the open-label study [SEP 360-322] for demographic (for all subjects) and EDE-Q modified (for subjects from SEP360-221), and height at the screening and the Endpoint assessment of the double-blind studies [SEP 360-221, or SEP 360-321] (for all subjects), otherwise).

As indicated in the protocol, height at the screening visit in the core studies will be carried over as OL Baseline. For operation convenience, the protocol specified that data collected at the EOT visit of the core studies are recorded in core studies only and are not to be saved in the clinical database of the extension study. Height at OL Baseline visit will be assigned a value per the corresponding Study Data Tabulation Model (SDTM) dataset of core studies directly.

Unless otherwise specified, at each study visit of study SEP 360-322, data derivation rule and missing imputation method for aggregated parameters that involves multiple individual items (eg, total score, subscale score, or composite score), are same as the corresponding ones in individual core study SAPs. DB Baseline is defined same as the Baseline in individual core study per core study SAPs. DB Baseline used in the analysis of study SEP 360-322 will be extracted from corresponding Analysis Data Model datasets (ADaM) of the core studies directly.

6.1.3.3. Withdrawal Baseline

See [Section 6.1.2.2](#) for the definition of Withdrawal Baseline. No imputation will be made if the Withdrawal Baseline value is missing.

6.1.4. Endpoint

6.1.4.1. Endpoint

Endpoint (ie, Week 52 Endpoint) is defined as the last post-OL Baseline assessment during the open-label treatment period.

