Breath Alcohol Test		Х		X			X	
12-Lead Electrocardiogram (ECG)				X	X	X	X	

Table 2: Schedule of Assessments (Continued)

Abbreviations: BSN = baseline; EOS = End of Study; EOT = End of Treatment; OL = open label; V = visit

^a Week 12 in core study. Baseline assessments indicated as "carried over" are primarily performed as part of Week 12 visit in the core study and do not need to be repeated; the data will be duplicated from Week 12 visit or other visits (such as for height) in the core study.

^b Subjects who discontinue from the study prior to completion of treatment with study drug will be asked to return to the site and complete the EOT assessments within 1 day of discontinuation and complete the Withdrawal Period visits and calls.

^c Subjects will take the first dose of study drug in this study on Day 1 (the morning following the baseline visit); there will be no break in study drug treatment between the core study and this extension study. All study drug will be administered by the subject once a day at approximately the same time each morning including on the days when clinic visits occur.

^d At the approximate midpoint between the scheduled monthly treatment period visits (ie, 14 ± 2 days after a visit), the site staff will contact the subject via telephone, text, or email to monitor for SAEs, AEs, and concomitant medications, as well as to remind subjects about adherence to study drug administration and upcoming visits, following which an unscheduled visit may be scheduled, if necessary.

Footnotes continued on the next page.

- ^e Informed consent will be obtained from all subjects after all procedures from the core study have been completed and before any study procedures unique to this study are performed.
- ^f Subjects must be fasting for at least 8 hours (may have water) prior to the indicated laboratory tests. Visits should be scheduled in the morning.
- ^g The "Since Last Visit" version will be used. Subjects who answer "yes" to "suicidal ideation" item 4 (active suicidal ideation with some intent to act, without specific plan) or item 5 (active suicidal ideation with specific plan and intent) on the C-SSRS assessment at any time during the study must be referred to the Investigator for follow up evaluation.
- ^h The Structured Interview Guide for the HAM-A (SIGH-A) will be used for the administration of the HAM-A.
- ⁱ The Structured Interview Guide for the MADRS (SIGMA) will be used for the administration of the MADRS.

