11.5.2.4. Visit 15E/End of Treatment (Week 52; Day 364 ± 1)

The following study related procedures will be performed:

- Record concomitant medications
- Perform physical and neurological examinations
- Collect vital signs and weight
- Perform ECG
- Record AEs
- Administer Scales: EDE-Q modified, SDS, MADRS, C-SSRS, BE-CGI-S, SF-12 (Subjects from Study SEP360-221 only), HAM-A, CSSA, and DESS
- Collect Samples for clinical laboratories (serum chemistry, lipid panel, hemoglobin A1c, hematology, urinalysis), UDS and urine pregnancy test for females of child bearing potential
- Perform breath alcohol test
- Perform study medication accountability

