- **Item 6:** Over the past 28 days, on how many **DAYS** have such episodes of overeating occurred (i.e., you have eaten an unusually large amount of food **and** have had a sense of loss of control at the time)?

322

See [Table 1](#) below for definition of rating data for EDE-Q, EDE-Q7, EDE-Q modified, and their relationship. [Table 2](#) provides the definition of frequency data for EDE-Q, EDE-Q modified, and their mapping relationship.

Table 1: Rating Data of EDE-Q, EDE-Q7, and EDE-Q modified Items

EDE-Q Modified Item	EDE-Q7 Item	EDE-Q Item	Abbreviated Content	Subscale
1	1	1	Restraint over eating	Restraint
		2	Avoidance of eating	
2	2	3	Food avoidance	
3	3	4	Dietary Rules	
		5	Empty stomach	
		7	Preoccupation with food, eating or calories	Eating Concern
		9	Fear of losing control over eating	
		19	Eating in secret	
		21	Social eating	
		20	Guilt about eating	
		6	Flat stomach	Shape Concern
		8	Preoccupation with shape or weight	
8	5	23	Importance of shape	
		10	Fear of weight gain	
10	7	26	Dissatisfaction with shape	
		27	Discomfort seeing body	
		28	Avoidance of exposure	
		11	Feelings of fatness	
7	4	22	Importance of weight	Weight Concern
		24	Reaction to prescribed weighing	
		8	Preoccupation with shape or weight	
9	6	25	Dissatisfaction with weight	
		12	Desire to lose weight	

[Reference: Fairburn C.G., 2014, EDE Edition 17.D, Cognitive Behavior Therapy and Eating Disorders\[1\]](#)

Table 2: Frequency Data of EDE-Q and EDE-Q modified Items

EDE-Q Modified Item	EDE-Q Item	Abbreviated Content
4	13	Times of unusually large amount of food
5	14	Times of having lost control eating
6	15	Days of overeating episodes
	16	Times of having made of sick for controlling shape or weight
	17	Times of having taken laxatives for controlling shape or weight
	18	Times of having exercised in a “driven” or “compulsive” for controlling shape or weight

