For EDE-Q, EDE-Q Modified, and EDE-Q7, the subscale scores are calculated as average of the corresponding individual scores. If any individual score of the subscale is missing, the corresponding subscale score will be set as missing and no imputation will be done. An EDE-Q global score is calculated as average of 4 EDE-Q subscale scores, an EDE-Q7 global score is calculated as average of 3 EDE-Q7 subscale scores, and an EDE-Q Modified global score is calculated as average of 3 EDE-Q Modified subscale scores. The EDE-Q global score, EDE-Q modified global score, and EDE-Q7 global score will be missing if any of corresponding subscale scores is missing. For EDE-Q, EDE-Q modified, and EDE-Q7, higher scores on the global score and subscale scores indicate greater levels of symptomatology; the global scores and subscale scores of EDE-Q Modified and EDE-Q7 are equivalent.

EDE-Q, EDE-Q7, and EDE-Q modified are all designed to collect the data in the past 28 days.

For subjects continued from study SEP360-221, EDE-Q modified is collected at open label baseline visit; for subjects continued from study SEP360-321, EDE-Q modified is carried over from W12/EOT visit in study SEP360-321. In addition, EDE-Q modified is collected at Weeks 4, 8, 12, 16, 20, 24, 28, 32, 36, 40, 44, 48, 52/EOT in the open-label treatment period.

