6.1.1.1. Open-Label Treatment Period (On Treatment)

The day of the 1st dose date in the extension study will be denoted as study Day 1. All measurements at each visit will be assigned a study day relative to this date. All data collected on/after Day 1 for subjects previously randomized to placebo group in core study or on/after the extension baseline visit for subjects previously randomized to dasotraline groups and up to Week 52, including the End-of-treatment/Early Withdrawal visit, will be considered within the open-label treatment phase. That is to say, the start of the open-label treatment period is defined as Day 1 for subjects previously randomized to placebo group and the OL Baseline visit date for subjects previously randomized to dasotraline groups; the end of the open-label treatment phase is defined as the maximum of the last date of administration of study medication and the withdrawal/ completion date.

The start and end of open-label treatment period are given below:

- **Start of treatment period** =
 - = Date of the first study medication administration for subjects previously randomized to placebo group
 - = Date of the OL Baseline visit for subjects previously randomized to dasotraline;
- **End of treatment period** = maximum of the last date of administration of study medication and the withdrawal/ completion date (ie, Week 52/EOT visit date).

Each subject's assessment at each visit in pre-treatment and treatment period will be assigned a study day with respect to the first dose date in the extension study.

- Study Day = Assessment date – the first dose date in the extension study + 1; if assessment date \geq the first dose date in the extension study
- Study Day = Assessment date – the first dose date in the extension study; if assessment date < the first dose date in the extension study

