Although all (scheduled and unscheduled) visits will be allocated to an analysis visit window, only planned protocol visits for each measurement will be included in the by-visit analyses. All tables and figures presenting data by visit will present only those timepoints where the applicable assessment was scheduled to be collected, unless otherwise noted below. Unscheduled and early termination data will be included for definition of endpoint or overall assessments (eg, the worst case analysis for an assessed period). Data listings will present all data, regardless of scheduled and unscheduled visits.

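### For EDE-Q modified items 4–6, an Endpoint form completed before Day 28 re-counts core-study days already in OL Baseline; a second Endpoint row starting at Day 22 would show how much this matters

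*SAP*

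**What the plan says.** **Recall period.** SAP 5.1.2 states: "EDE-Q, EDE-Q7, and EDE-Q modified are all designed to collect the data in the past 28 days". Item 6, the number of binge days, begins "Over the past 28 days, on how many". Item 4 uses the same period, and item 5 refers back to item 4.

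**Schedule.** After OL Baseline, "EDE-Q modified is collected at Weeks 4, 8, 12, 16, 20, 24, 28, 32, 36, 40, 44, 48, 52/EOT". Nothing is scheduled at Week 2, so the first planned form (Day 28 ± 3) fits the recall period.

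**Early stoppers.** Footnote b to Protocol Table 2 asks them to "complete the EOT assessments within 1 day of discontinuation"; Protocol 13.2 says only that this should happen as soon as possible. The End of Treatment visit (Protocol 11.5.2.4) includes the questionnaire: "Administer Scales: EDE-Q modified, SDS, MADRS, C-SSRS, BE-CGI-S".

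**Endpoint.** SAP 6.1.1.1 ends the open-label period at the "maximum of the last date of administration of study medication and the withdrawal/ completion date", so the early-termination visit lies inside it. SAP 6.1.2.1 adds: "Unscheduled and early termination data will be included for definition of endpoint or overall assessments". Under SAP 6.1.4.1 the Endpoint "is defined as the last post-OL Baseline assessment during the open-label treatment period". Protocol 15.3.2 has the same idea. Neither document sets a minimum study day.

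**Use.** SAP 7.2.2 reports Endpoint values, changes from DB and OL baseline, and a table of item 6 day categories that starts at zero days.

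**The concern.** For a subject who stops before Week 4, the End of Treatment form is normally the only post-baseline EDE-Q modified form, and it becomes the Endpoint. Its 28-day window reaches back past Day 1 into the core study, over days that the OL Baseline form has already counted. Three results follow for items 4–6:

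- Apart from recall error, the shared days add the same count to both forms. They contribute nothing to the change from OL Baseline and pull it toward zero.
- In Pbo-Das, the Endpoint level and the item 6 category include placebo days. A subject with no binge days on open-label drug cannot fall in the zero-day category if there were any in the carried-in days.
- In Das-Das, the carried-in days are core-study dasotraline days.

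The SAP's visit windows already keep such forms out of the by-visit tables. Days 1–21 map to Week 2, and those tables show only timepoints at which the scale was scheduled. The same forms enter the Endpoint row without a flag. The issue is particular to the long recall: BE-CGI-S looks back only 7 days (Protocol 11.3.3).

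**Working it through.** The plan states no figure on this point, so there is none to reproduce. The check is a count of calendar days.

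**Inputs.** Recall of 28 days (SAP 5.1.2). OL Baseline on Day −1, Day 1 the next morning, no treatment break (Protocol 7.1 and Table 2, footnote c). No Day 0 (SAP 6.1.1.1). Form completed on Day v.

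**Shared days.**
- If the visit day counts in the recall, OL Baseline covers Days −28 to −1. The later form covers Days 1 to v plus the 28 − v days before Day 1, all of them in the OL Baseline window. Shared = 28 − v.
- If the visit day does not count, OL Baseline covers Days −29 to −2. The later form covers v − 1 open-label days and 29 − v earlier days, of which Day −1 is not in the OL Baseline window. Shared = 28 − v again.

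| Form on Day | Shared days | Share of 28 |
|---|---|---|
| 7 | 21 | 75.0% |
| 10 | 18 | 64.3% |
| 13 | 15 | 53.6% |
| 14 | 14 | 50.0% |
| 21 | 7 | 25.0% |
| 22 | 6 | 21.4% |
| 25 | 3 | 10.7% |
| 28 | 0 | 0% |

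More than half of the days are shared only through Day 13. Averaged with equal weight over Days 2–27, the share is 13.5/28 = 48%.

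**One subject (assumed rates, for illustration).** A Pbo-Das subject has 4 binge days a week on placebo and 1 a week on drug from Day 1, with a form on Day 14 and the visit day counted. OL Baseline: 28 × 4/7 = 16. Recorded Endpoint: 14 × 4/7 + 14 × 1/7 = 8 + 2 = 10, a change of −6. A full 28-day window at the on-drug rate would give 28 × 1/7 = 4, a change of −12. The lost half equals the 50% overlap.

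**Group mean (assumptions).** Let a fraction p of Endpoint values be affected, with average overlap s and the same full-window change Δ in everyone. The mean change is then (1 − p)Δ + p(1 − s)Δ = Δ(1 − ps). The documents do not give p. For p from 2% to 15% (10 to 75 of about 500) and s from 25% to 75%:
- lowest: 0.02 × 0.25 = 0.5%
- middle: 0.05 × 0.50 = 2.5%; 0.10 × 0.50 = 5%
- highest: 0.15 × 0.75 = 11.25%

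**Scheduled visits.** A Week 4 visit at the early edge of the protocol window (Day 25) shares 3 of 28 days. A form at the early edge of the SAP Week 4 window (Day 22) shares 6.

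**The case against.** The case against concedes the mechanism and disputes its size and reach. Most of it stands.

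- **Consequence.** Effectiveness is a secondary objective, the analysis is descriptive with no hypotheses, scheduled visits use observed cases, and the documents rest no decision on the Endpoint row.
- **Number affected.** Subjects are only asked to return, some will be lost to follow-up, and a field may be blank. Any count based on early stopping is therefore an upper bound. SAP 7.1.4 already tabulates exposure of 1–13 and 14–27 days, disposition is reported, and all data are listed. What is missing is a count specific to this questionnaire.
- **The example.** It is a favourable case: a high binge rate after 12 weeks of placebo, full effect from Day 1, and comparison with 28 on-drug days that the subject never had. It illustrates the arithmetic and does not estimate an effect.
- **Form date.** Overlap follows the form date, not the stop date. A late form shares fewer days but takes in days off drug.

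A reader might also infer three stronger things that the documents do not support. First, that the Endpoint of anyone stopping before Day 28 is mostly core-study time: from Day 14 the shared part is half or less. Second, that all EDE-Q modified scores are distorted to this degree: the global and subscale scores average 0–6 ratings, including the importance of weight and shape and dissatisfaction with them, and the day count does not carry over to those. Third, that early forms should be dropped from the Endpoint: that would replace dilution with selection and depart from the definition in Protocol 15.3.2, whereas SAP Section 4 declares no change from the protocol.

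The objection does not remove the main point. No rule in either document excludes, flags or rescales a form with a short open-label window.

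**Conclusion.** The point holds for items 4–6, including the item 6 category table. An Endpoint form on Day v < 28 repeats 28 − v of the OL Baseline days. This moves the change from OL Baseline toward zero and, in Pbo-Das, mixes placebo days into the Endpoint categories. The overlap follows from the schedule and the recall period and needs no assumption beyond subjects answering as the form asks.

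The effect on the group mean is uncertain. The 0.5–11% range rests on assumed dropout and a constant effect. The number affected to any material degree is at most the subjects with under 28 days of exposure who return a usable form. Beyond those, a subject whose last form is a Week 4 form on Days 25–27 shares at most 3 days.

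It is a small improvement to a secondary, descriptive summary. The primary safety objective is not touched.

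**What to change.** Leave the protocol-defined Endpoint row as it is. In SAP 6.1.4.1 and 7.2.2, for EDE-Q modified items 4–6 and the item 6 category table, add a second Endpoint row that uses only forms on or after Study Day 22. Beside it, give the number of subjects in each analysis group whose only post-OL form is earlier. Describe this in the SAP as an added supportive summary, and note it in Section 4 so that the statement there remains accurate.

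Day 22 is the start of the SAP's own Week 4 window (Days 22–35), so no form can count in the Week 4 row and yet be barred from the new Endpoint row. At most 6 of 28 days (21%) are then shared.

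The cost is a few SAP sentences and one extra row per table, with no new data and no change in conduct. The new row has a slightly smaller N and leaves out the earliest stoppers, which is why both rows should be shown.
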